10.2 Planned recruitment rate

Recruitment across 3 sites will allow access to approximately 150 new IBD cases/year (187 cases over 15 months) and also allow us to explore regional differences in VOC profiles. Given the broad eligibility criteria and non-invasive nature of the study, we expect that we can achieve the required participation rate of 77% to recruit 143 IBD cases in 15 months (3-4 IBD cases/centre/month). We will recruit a similar number of non-IBD controls over the same time period.

10.3 Statistical analysis plan

10.3.1 Summary of baseline data and flow of patients

We will summarise the demographic, clinical and environmental characteristics of the children recruited to the study using simple descriptive statistics. Continuous variables will be summarised according to number of subjects with non-missing data as mean, standard deviation, median, minimum, and maximum. Categorical variables will be summarised according to the absolute frequency and percentage of subjects in each category level. The denominator for the percentages is the number of subjects with data available unless noted otherwise.

10.3.2 Primary outcome analysis

For the VOCS identified by GCMS, consistent with our findings in adults (Ahmed 2016), we anticipate identifying a small number of VOCs that can be used to diagnose IBD and distinguish IBD from other common pathologies including functional abdominal conditions.

For the results generated by the GC-sensor (Odoreader©), we will compare the faecal VOC profile in children in whom IBD is confirmed with that in children with alternative diagnoses according to the advanced statistical methods required for determining and comparing VOC profiles (Aggio 2016).

10.3.3 Secondary outcome analysis

Similar analyses as for the primary outcome will be used for the secondary outcomes. To shed light on underlying disease mechanisms in pIBD and other common conditionse will use existing KEGG databases to determine the source of faecal VOCs identified by GCMS, which will include bacteria, fungi, host tissues and metabolism (http://www.genome.jp/kegg/kegg2.html).

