3.5 Secondary endpoints/outcomes

1. Faecal VOCs according to IBD diagnosis, distribution and severity at initial presentation

A diagnosis of IBD will be based on gastrointestinal endoscopy and biopsy and imaging. IBD type will be classified according to standard clinical guidelines (Levine 2014). The distribution of disease and associated manifestations (e.g. presence of fistulas) in CD will be classified according the Paris classification (Levine 2011). The severity of IBD at initial diagnosis will be graded according to paediatric-specific disease activity scores: weighted Paediatric Crohn's Disease Activity Index (wPCDAI) and Paediatric Ulcerative Colitis Activity Index (PUCAI; Ruemmele 2014).

2. Faecal VOCs in children with IBD according to response to treatment at 3 months after diagnosis

Treatment of IBD will follow established clinical guidelines. After 3 months of treatment, faecal VOCs will be compared in children who have and have not achieved clinical remission. Clinical remission in CD will be defined as a wPCDAI \leq 12.5 and in UC as PUCAI <10 points in the absence of corticosteroid treatment (Ruemmele 2014).

3. Analysis of faecal fungi in relapse of IBD

A change in the faecal mycobiome may be associated with relapse of IBD, as indicated by the presence of fungal metabolites amongst the VOCs reported in adults with Crohn's disease. If presence, this would open new avenues of treatment based on probiotics and or antifungals. VOCs may be used to monitor the effect of such therapy.

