The data (chromatograms and fragmentation patterns) will be analysed using AMDIS software and the current NIST library of over 240,000 compounds. Project–specific libraries of compounds will be used to generate reports for each group of children – those with CD, UC and other pathologies. Metab software (Aggio 2011) will be used to align the reports. Metaboanalysis software (Xia 2009) will be used to compare the abundance of each VOC in each group: the software will report the false discovery rate (FDR) allowing comparison of datasets of this kind. ANOVA will be performed in the same way. We will produce summaries of the data describing the fold changes, FDR, sensitivity, specificity and ROC curves for compounds and models derived from them. This method uses equipment that is available in hospital clinical chemistry laboratories.

For the second method, the stool sample will be analysed by our GC-sensor (Odoreader©). This is more rapid than the first method and generates a VOCs profile (rather than identifying individual VOCs). 450mg of faeces are heated within the device, and the emitted gases passed through a GC column. On leaving the column, the VOCs pass perpendicular to a metal oxide sensor unit. A current is passed across the sensor and its resistance is determined by the presence of VOCs. Consequently the sensor output (current) is a representation of the VOCs in the sample (with an output similar to a chromatogram). We have a well-defined algorithm that removes the baseline, normalises the data and performs retention time correction before comparing the profiles derived from two groups of samples using wavelets. The data is then reported as sensitivity, specificity and AUROC of a model using state of the art modelling tools including support vector machine polynomial (SVMpoly) with double cross validation and Monte Carlo randomisation (Aggio 2016).

Stool samples will be stored frozen for up to 5 years for possible use in ancillary studies. Stool samples collected from participants as part of this study will be transported, stored, accessed and processed in accordance with national legislation relating to the use and storage of human tissue for research purposes and such activities shall at least meet the requirements as set out in the 2004 Human Tissue Act and the 2006 Human Tissue (Scotland) Act.

In the version of the protocol, we will also investigate the fungal mycobiome.

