10.1 Sample size calculation

Given the high sensitivity of FC in identifying children with IBD (0.98; 95% CI 0.95–1.0; Henderson 2014), we have based the sample size calculation on demonstrating that faecal VOCs have a higher specificity in identifying IBD than FC. We require 88 children with suspected IBD to demonstrate that VOCs has a better specificity of 0.80 than the specificity of 0.68 reported for FC (Henderson 2014) with 80% power at the 0.05 significance level.

Given the non-invasive nature of our study, we plan to increase the number of children recruited to also assess the ability of VOCs to differentiate between CD and UC. We plan to exceed the numbers of adults with active IBD that demonstrated excellent separation between CD and UC in our previous study (110 patients; Ahmed 2016). Our hospital IBD databases indicate that amongst new cases, two-thirds have CD and one-third UC. In our clinical experience, IBD is confirmed in 1 in 2 children with suspected IBD. To achieve sufficient power, we will recruit a total of 286 children with suspected IBD.

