10.4 Subgroup analyses

We will fully explore the data from our non-IBD children to identify characteristic faecal VOC profiles in common diagnostic groups (e.g. functional abdominal pain, coeliac disease) and also demographic and environmental factors (e.g. age, sex, diet) using the approaches described above.

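### Only group-comparison methods are named for IBD severity, although it is measured by numerical scores; a full-scale GC-MS analysis would be a cheap gain in power

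*Protocol*

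**What the plan says.** Protocol 3.2 asks, among other things, whether VOCs at presentation can tell apart the severity of IBD. Protocol 3.5 sets the measure: "The severity of IBD at initial diagnosis will be graded according to paediatric-specific disease activity scores", namely wPCDAI and PUCAI. The only score cuts in the protocol are the month-3 remission thresholds (wPCDAI ≤12.5, PUCAI <10); none is given for severity at diagnosis.

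For the analysis, 10.3.3 states: "Similar analyses as for the primary outcome will be used for the secondary outcomes". The primary analysis (10.3.2) sets confirmed IBD against other diagnoses, with the methods described in 7.11:

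- **GC-MS:** abundance of each VOC compared between groups with a false discovery rate, ANOVA, and sensitivity, specificity and ROC curves.
- **GC-sensor:** an algorithm that "performs retention time correction before comparing the profiles derived from two groups of samples using wavelets", reported as sensitivity, specificity and AUROC of a cross-validated classifier.

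No section names a correlation or regression of VOCs on an activity score. For the non-IBD children, 10.4 will explore "demographic and environmental factors (e.g. age, sex, diet) using the approaches described above".

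**The concern.** A numerical score can enter a group comparison only as groups, and a two-group classifier needs a binary label. Grouping discards the ordering within each group and the spread of the score, and the result then depends on where the line is drawn. The severity groups are small, and because each disease has its own score they cannot simply be pooled. A real relation between a VOC and severity could be missed and then reported as a negative answer to a stated secondary objective.

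**Working it through.** **The plan's own figure.** The protocol states no power for severity. Its one calculation (10.1) concerns specificity: "We require 88 children with suspected IBD" to show that "VOCs has a better specificity of 0.80 than the specificity of 0.68 reported for FC", "with 80% power at the 0.05 significance level". A one-sample comparison with a fixed 0.68, two-sided, with the variance taken at 0.80, gives (1.960 + 0.842)² × 0.80 × 0.20 / 0.12² = 87.2, rounded up to 88. The figure reproduces but does not bear on severity.

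**Inputs.** From 10.1 and 10.2: 286 children in total, 143 with IBD, two-thirds CD and one-third UC. So 143 × 2/3 ≈ 95 CD and 143 × 1/3 ≈ 48 UC. Not in the protocol, and therefore assumed: one VOC and the score are bivariate normal with correlation r between 0.10 and 0.50; two-sided alpha 0.05; the score is cut 50/50, 33/67 or 25/75.

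**Formulas.** Full-score power is Φ(atanh(r)·√(n−3) − 1.960). Cutting a normal score with a fraction p on one side multiplies the correlation by a = φ(z_p)/√(p(1−p)), where z_p is the normal quantile at p. This gives a = 0.798 at 50/50, 0.770 at 33/67 and 0.734 at 25/75. Grouped power uses a·r in place of r.

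**Example, CD at r = 0.30.** Full score: 0.3095 × √92 − 1.960 = 1.009, so power is 84.3%. Median split: a·r = 0.239, and 0.244 × 9.592 − 1.960 = 0.38, so power is 64.9%.

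| Group | r | Full score | 50/50 | 33/67 | 25/75 |
|---|---|---|---|---|---|
| CD, n = 95 | 0.10 | 15.9% | 11.6% | 11.1% | 10.5% |
| CD | 0.20 | 49.4% | 33.9% | 31.9% | 29.4% |
| CD | 0.30 | 84.3% | 64.9% | 61.7% | 57.4% |
| CD | 0.50 | 100.0% | 98.2% | 97.3% | 95.8% |
| UC, n = 48 | 0.10 | 9.9% | 7.7% | 7.5% | 7.1% |
| UC | 0.30 | 54.6% | 37.4% | 35.1% | 32.3% |
| UC | 0.40 | 81.1% | 60.2% | 57.0% | 52.7% |

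**Loss as a function of full-score power.** To free the result from one choice of r and n, set t = 1.960 + z_P, where z_P is the normal quantile of the full-score power P. Grouped power is then about Φ(a·t − 1.960). At P = 50%, 80% and 90%:

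- 50/50 cut: loss of 15.4, 19.2 and 16.6 points
- 33/67 cut: 17.4, 22.2 and 19.6 points
- 25/75 cut: 19.9, 26.2 and 23.8 points

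At P = 99% the loss falls to 6.2 to 10.8 points. The shortcut slightly understates the loss at larger r: the direct figure for UC at r = 0.40 with a 25/75 cut is 81.1 − 52.7 = 28.4 points.

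**More than two groups.** Three equal groups compared by ANOVA (noncentral F) lose about as much: CD at r = 0.30, 85.8% for the linear test against 66.0%; UC at r = 0.40, 84.1% against 62.3%.

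**Stricter threshold.** At alpha 0.001, a rough stand-in for control over many VOCs, CD at r = 0.40 goes from 78.0% to 45.3% with a median split.

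**Age (10.4).** With about 143 non-IBD children and r = 0.25, the figures are 85.6% against 66.7% for a median split.

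**The case against.** The strongest case against is that the protocol never writes down a cut. A reader might infer that the scores and age must be dichotomised and that a fixed loss of power follows. The text does not go that far:

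- 10.3.3 says the analyses will be similar, not identical. No cut-point, number of severity groups or age band appears.
- Severity is to be graded and the objective is to distinguish it, so a comparison of grades with sensitivity and specificity is a legitimate question in a diagnostic study. The source cited for the grading is not at hand, so published grades cannot be ruled out.
- A separate SAP is announced in section 10, and 10.9 allows other methods. The SAP may settle the scale.
- Age is one bracketed example in an exploratory paragraph, and 10.9 also puts age in regression models.
- The power figures rest on one normally distributed VOC, not on the multivariate sensor classifier.

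Most of this stands, and it limits the claim. What remains is that the protocol does state a family of methods for severity, and every member of it compares groups. If grading means categories, the grouping is confirmed, and three groups lose about as much as two. The latitude in 10.9 sits with the analyses that combine diagnostic tests and is not a plan for severity. The regression models there concern the diagnosis of IBD, so they do not answer how VOCs vary with age among children who all lack IBD.

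**Conclusion.** The point holds as a cheap improvement. For severity at presentation the protocol names only group comparisons, two-group for the sensor, with no baseline cut, although the measures are numerical scores in about 95 CD and 48 UC children. For a single VOC, grouping costs roughly 15 to 26 points of power where the full-score test would have 50% to 90%. Over all the correlations assumed, the range at alpha 0.05 is about 0 to 28 points. These figures depend on an assumed correlation, cut and normal distribution, since the protocol gives no effect size. No loss was computed for the sensor classifier. The severity objective is secondary and carries no stated power, so neither the 88 nor the 286 is affected. Age under 10.4 is a minor, exploratory matter.

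**What to change.** - **10.3.3, GC-MS:** make the main severity test a linear or rank regression of each VOC's abundance on the full score, separately in CD (wPCDAI) and UC (PUCAI), with the same FDR control.
- **Comparison by grade:** keep it, with sensitivity, specificity and ROC curves, as a supporting analysis.
- **GC-sensor:** a regression form of the cross-validated model is optional.
- **Month-3 remission comparison:** leave unchanged.
- **10.4:** where age is explored in non-IBD children, enter it as a continuous variable.

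The cost is a few sentences and a modest amount of analysis code, with no new patients or data. The downside is that the main severity result is reported as slopes or correlations rather than as sensitivity and specificity.

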10.4 Subgroup analyses

We will fully explore the data from our non-IBD children to identify characteristic faecal VOC profiles in common diagnostic groups (e.g. functional abdominal pain, coeliac disease) and also demographic and environmental factors (e.g. age, sex, diet) using the approaches described above.

10.5 Adjusted analysis - N/a

10.6 Interim analysis and criteria for the premature termination of the trial: N/a

10.7 Subject population

All participants in whom analysis of faecal VOCs is completed will be included in the study analysis.

The analysis of faecal VOCs according to response to treatment in IBD will include all children diagnosed with IBD in whom faecal VOCs are analysed 3 months after treatment.

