7.5 Unblinding: N/a

7.6 Baseline data

Demographic, environmental and clinical information will be collected onto standard forms:

- Demographic information will include age, gender, ethnicity
- Clinical information will include anthropometry, main presenting gastrointestinal symptoms and signs, current diet (e.g. vegan), current medication, treatment with oral/parenteral antibiotics or anti-fungal agents in the last 3 months
- Environmental factors will include: number of siblings at home, smoker in the household, household pets, urban/rural residence, foreign travel in last 3 months

The results of routine clinical baseline investigations if done will be recorded:

- In blood: haemoglobin, white cell count, inflammatory markers (platelets, C-reactive protein, ESR), albumin, liver function tests, urea, creatinine, test for coeliac disease
- In stool: calprotectin, C. difficile toxin, bacterial culture
- Imaging: X rays and scans

Further investigations will be planned according to the initial clinical assessment in accordance with usual clinical practice.

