7.7 Trial assessments

A diagnosis of IBD will be based on gastrointestinal endoscopy and biopsy and imaging and IBD type classified according to standard clinical guidelines (Crohn's disease, ulcerative colitis, indeterminate colitis; Levine 2014). The distribution of disease and associated manifestations (e.g. presence of fistulas) in CD will be classified according the Paris classification (Levine 2011). The severity of IBD at initial diagnosis will be graded according to paediatric-specific disease activity scores: weighted Paediatric Crohn's Disease Activity Index (wPCDAI) and Paediatric Ulcerative Colitis Activity Index (PUCAI; Ruemmele 2014). Treatment of IBD will be provided by clinical staff and follow established clinical guidelines.

For other conditions, specific investigations and diagnosis will be guided by clinical assessment; e.g.

Faecal volatiles in children with inflammatory bowel disease

serum anti-tissue transglutaminase antibodies and/or small bowel biopsy for the diagnosis of coeliac disease; stool bacterial culture for infectious diarrhoea. Appropriate treatment will be provided by clinical staff.

The clinical records of all children will be reviewed at 3 months after recruitment and information regarding results of investigations and diagnosis/diagnoses will be recorded.

In children with IBD, a further stool sample will be requested at 3 months. This will be used for measurement of faecal calprotectin as part of routine clinical care and, if young people or parents/guardians agree, for repeat measurement of VOCs as described above. Treatment received will be recorded and current disease activity determined. Clinical remission in CD will be defined as a wPCDAI ≤12.5 and in UC as PUCAI <10 points in the absence of corticosteroid treatment (Ruemmele 2014).

- 7.8 Long term follow-up assessments: Participants will not be followed-up after 3 months.
- 7.9 Qualitative assessments Nested studies: N/a
- 7.10 Withdrawal criteria: N/a

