10.8 Procedure(s) to account for missing or spurious data

Maximum efforts will be made to avoid missing values in the database. However, where this does occur, missing covariates will be imputed using simple imputation methods in the covariate adjusted analysis based on the covariate distributions. For a continuous variable, missing values will be imputed from random values from a normal distribution with mean and SD calculated from the sample. For a categorical variable, missing values will be imputed from random values from a uniform distribution with probabilities P1, P2, ..., and Pk from the sample. For count data, missing values will be imputed from random values from a Poisson distribution with λ from the sample. Seed for the imputation is set as 128.

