10.9 Other statistical considerations

In addition to the main analyses described above, we also plan to undertake extensive statistical analysis to explore whether combining VOC data with faecal calprotectin and possibly other inflammatory markers (e.g. CRP) increases sensitivity and specificity in the diagnosis of IBD. Multivariate logistic regression models will be used to determine the specificities and 95% confidence intervals of combinations of diagnostic tests and also explore the effects of demographic factors such as age, sex and region. Other statistical methods will be used if deemed necessary.

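### Section 10.5 rules out the adjusted analysis that 10.8 presupposes, and the month-3 remission comparison cannot separate corticosteroid effects on VOCs from disease activity

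*Protocol*

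**What the plan says.** Protocol section 10.5 is a single entry: "10.5 Adjusted analysis - N/a". Section 10.8 then states that "missing covariates will be imputed using simple imputation methods in the covariate adjusted analysis based on the covariate distributions", and gives the imputation distributions and a fixed seed. Section 10.9 adds logistic models of combined diagnostic tests, which will also "explore the effects of demographic factors such as age, sex and region"; it presents these as extra to the main analyses. Item C of the study timeline schedules an analysis joining the VOC profile to demographic, clinical and environmental data, without giving its form.

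For month 3, section 3.5 says: "After 3 months of treatment, faecal VOCs will be compared in children who have and have not achieved clinical remission". Section 10.3.3 applies methods similar to those for the primary outcome and names no treatment term. Sections 3.5 and 7.7 define remission in CD by a wPCDAI threshold and in UC as "PUCAI <10 points in the absence of corticosteroid treatment". Section 7.7 also says "Treatment received will be recorded and current disease activity determined", and Appendix 4 lists previous and current treatment at visit 2. At baseline, section 7.6 records age, sex and "treatment with oral/parenteral antibiotics or anti-fungal agents in the last 3 months".

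**The concern.** An analysis that is not applicable needs no missing-data rule. A SAP written from this protocol must depart from either 10.5 or 10.8, and once results are known that choice could be made on the results. Section 10.5 is a positive statement, so this is not a detail simply left for the SAP.

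The practical harm is at month 3. The remission label there mixes disease activity with treatment status. If corticosteroids alter a VOC, directly or through the microbiota, that VOC will differ between the two groups even when it carries no information on disease activity. Under the plan as written it could be reported as a marker of persistent disease. A test built on it would partly detect who is taking steroids, which the clinician already knows.

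**Working it through.** **The plan's own figures.** The protocol gives no number for this point. Its one powered figure, 88 children for specificity 0.80 against 0.68, reproduces as (1.960 + 0.842)² × 0.80 × 0.20 / 0.12² = 87.2, rounded up. It contains no covariate and does not bear on the issue.

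**The passages side by side.**
- 10.5: no adjusted analysis.
- 10.8: a covariate-adjusted analysis exists and has an imputation procedure. This is a direct conflict.
- 10.9: exploratory models with age, sex and region, additional to the main analyses. These can coexist with unadjusted main analyses, but 10.5 does not say so.
- Timeline item C: a combined analysis of unspecified form, whose relation to 10.5 is likewise unclear.
- 10.3.3 with 3.5: month-3 VOCs compared by remission status, with no treatment term.

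**Size at month 3, clause covering CD and UC.** From the protocol: 143 IBD cases (10.2). Assumed, because the documents give no values: 43 not in remission and 100 in remission; 14 to 29 children on steroids, all among the 43; a steroid shift of 0.5 SD in one VOC that is otherwise unrelated to remission; VOC SD of 1; every child supplying a month-3 sample.
- Standard error of the difference: √(1/43 + 1/100) = 0.182 SD.
- Spurious difference: (14/43) × 0.5 = 0.163 SD to (29/43) × 0.5 = 0.337 SD.
- z: 0.163/0.182 = 0.89 to 0.337/0.182 = 1.85.
- Two-sided rejection rate at nominal 5%, Φ(z − 1.96) + Φ(−z − 1.96): 14.5% (about 15%) to 46%.

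**Clause covering UC only.** Further assumptions: one-third of steroid users have UC (the UC share of new cases in 10.1) and all of these are non-remitters; steroid use in CD is unrelated to remission, so CD users split 43:100.
- 14 users: 4.67 UC and 9.33 CD. Non-remission (4.67 + 2.81)/43 = 17.4%; remission 6.53/100 = 6.5%. Difference 0.109 × 0.5 = 0.054 SD, z = 0.30, rejection rate about 6%.
- 29 users: 9.67 UC and 19.33 CD. Non-remission (9.67 + 5.81)/43 = 36.0%; remission 13.52/100 = 13.5%. Difference 0.225 × 0.5 = 0.112 SD, z = 0.62, rejection rate about 9%.

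**Sensitivity to the assumptions.** A separate calculation used 143 cases, half in remission, and a general treatment used by different proportions of the two groups, with a VOC shift of 0.3 to 0.8 SD. The rejection rate was 5.4% to 7.3% for 50% against 40% treated, 8.3% to 26.9% for 60% against 30%, and 14.4% to 61.9% for 70% against 20%. With no imbalance it stayed at 5.0%.

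**The case against.** The strongest reply is that much of this is exploratory, that detail goes to a separate SAP (section 10), and that unadjusted accuracy among children with suspected IBD from the same clinics is a legitimate target. That stands for the primary contrast. A reader might infer that the primary result is invalid without adjustment for age and antibiotics. The documents do not support this: the question is diagnostic discrimination, 10.9 explores age in additional models, and timeline item C foresees joining VOC profiles to data that include recent antibiotics. Nor does 10.9 squarely contradict 10.5, since it is declared additional.

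Three further inferences should be resisted.
- Dietary therapy does not act as steroids do here. Diet is no part of the remission definition, so no child is placed in either group by it; the baseline exclusion of treated children says nothing about VOCs.
- It is tempting to credit adjustment for baseline VOCs with the precision gain familiar from randomised trials. Remission groups are self-formed and may differ at baseline, so conditioning changes the question as well as the variance. The stated objective asks whether month-3 VOCs distinguish remission.
- The false-positive rates are not predictions. The steroid condition is attached most directly to UC, month-3 VOC sampling is optional, and section 7.11 reports false discovery rates.

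A regression term for steroids would also be a weak remedy. Where the clause applies, no child in remission is on steroids, so the term is estimated among non-remitters only. It would not fit the Odoreader classifier either. Both points argue for restriction rather than regression.

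What the reply does not answer is the conflict between 10.5 and 10.8, or the absence of a treatment term in a comparison whose grouping depends on treatment.

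**Conclusion.** The point holds in two parts. First, 10.5 and 10.8 contradict each other in the current text, and the standing of 10.9 and timeline item C beside 10.5 is unclear. Second, wherever the steroid clause applies, the month-3 comparison as planned cannot separate a corticosteroid effect on VOCs from disease activity. That follows from the remission definition and needs no numerical assumption beyond some steroid use at month 3.

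The size does need assumptions. Under those in the working, the per-VOC false-positive rate is about 15% to 46% if the clause covers both diseases and about 6% to 9% if it covers UC only, before false discovery rate control. The documents support neither a single figure nor the claim that a false marker will be reported. The matter should be settled before the VOC data are analysed; it does not threaten the primary accuracy estimate.

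**What to change.** 1. Replace the entry in 10.5 with a statement that agrees with 10.8 and 10.9: which analyses are unadjusted, which are adjusted, with which covariates, and to which of them the 10.8 imputation applies. Say where the combined analysis in timeline item C belongs.
2. State in 3.5 and 7.7 whether the corticosteroid clause covers CD as well as UC. The definition itself is a clinical matter and is not questioned here.
3. Keep the month-3 comparison as planned, and pre-specify a second analysis restricted to children not on corticosteroids at month 3, reported by IBD type. It works for both GCMS and Odoreader data. Limit any remission-marker conclusion to VOCs that persist there.
4. For the primary contrast, keep the unadjusted accuracy. As a supplementary analysis, report the VOC score's discrimination beyond age, sex, centre and antibiotics in the last 3 months.

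The cost is wording, a little more analysis, and a smaller month-3 sample in the restricted analysis. No new data are needed. Under the working's assumptions (clause covering both diseases), the non-remission group falls from 43 to between 29 and 14. The standard error rises from 0.182 to √(1/29 + 1/100) = 0.211 or √(1/14 + 1/100) = 0.285 SD, a factor of 1.16 to 1.56. A VOC that fails to persist may therefore reflect low power, and the report should give estimates with confidence intervals alongside any test.
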